8.2.12. Prostate Cancer Biopsies

A listing of data for biopsies performed to confirm prostate cancer will be provided.

8.2.13. Suicidality Assessment

Assessment of suicidality will be done using the Columbia Suicide Severity Rating Scale (C-SSRS) and is scheduled to be assessed at each Screening, Month 6, Month 12, and Month 24 (or end of treatment) visits. Tabular summaries of suicidal ideation and suicidal behavior will be produced at each of the scheduled assessments. Along with the aforementioned tabular summary, as well, for all subjects with suicidal ideation or behavior at any assessment, a listing of C-SSRS data will be provided (as a table), along with listings of details of suicidal ideation and suicidal behavior.

In addition a listing of C-SSRS assessments for all subjects will be provided. As noted in the adverse event section of this document, the possible suicidality-related adverse events will be produced.

8.3. Health Outcomes Analyses

Health outcomes analyses will be in terms of: BPH Impact Index (BII), BPH-Related Health Status (BHS), and the Problem Assessment Scale of the Sexual Function Inventory (PAS SFI). Health outcomes analyses will be performed using the ITT population unless otherwise specified in text or data display shells.

A list of planned Health Outcomes data displays is in [Appendix 15: List of Data Displays](#). Baseline and change from baseline are defined in [Appendix 6](#). Last observation carried forward (LOCF) and At Visit approaches are defined in [Appendix 7](#). Reference [Appendix 11](#) for descriptions of handling multiplicity.

8.3.1. BPH Impact Index

The BPH Impact Index (BII) consists of four questions. It is administered at screening, baseline and at each of the scheduled post-baseline treatment phase visits. The BII total score is the sum of the four questions; the total score range is 0 to 13. BII summaries and analyses will be in terms of the total (score); exceptions will be noted such as for supporting summaries of individual questions.

For calculation of the BII total, missing individual responses will be imputed when at least two of the four questions are answered (nonmissing). For the imputation, the average of the nonmissing responses will be calculated and rounded to the nearest integer. This average will be imputed for the original missing response(s). If at least 20% of the subjects have at least one imputed BII then the statistical analyses will be repeated based on non-imputed scores.

Total BII, change from baseline BII, and percentage change from baseline BII will be summarized by treatment group using both the LOCF and At Visit approaches at each scheduled post-baseline assessment. Change from baseline BII at each scheduled post-baseline assessment will be compared in terms of combination treatment versus

tamsulosin treatment using t-tests from a general linear model (GLM) with effects for treatment, cluster, and baseline BII. Two-sided tests at 0.05 level of significance will be conducted.

The adjusted mean estimates (mean and standard error), the adjusted mean difference, and the 95% confidence interval in terms of the adjusted mean difference will be presented. The adjusted mean difference will be in terms of combination treatment minus tamsulosin treatment. The model results will be presented on same tabular summary as the arithmetic mean, standard deviation, median, minimum and maximum. The results will be presented by treatment for each scheduled post-baseline assessment.

BII adjusted mean change from baseline will be plotted by treatment for each post-baseline scheduled visit in terms of each LOCF and At Visit approach.

Each of the four BII individual question responses will be summarized at Baseline, Month 12, and Month 24 by treatment group. Month 12 and Month 24 changes from baseline will be summarized by treatment group for each of the four questions. The summaries will be based on the ITT population and presented using both LOCF and At Visit approaches. No statistical testing will be performed.

Listings of BII individual question and total scores will be presented.

As a supportive analysis, BII will be analyzed using a mixed-model repeated-measures (MMRM) analysis in a manner similar to that described for primary efficacy in [Appendix 13](#).

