7. PRIMARY STATISTICAL ANALYSES

7.1. Primary Efficacy Analyses

7.1.1. Overview of Planned Primary Efficacy Analyses

The primary efficacy parameter after the 2nd year of the study is change from baseline IPSS (International Prostate Symptom Score). The IPSS questionnaire consists of seven questions with each question score ranging from 0 to 5. It is administered at screening, baseline, and at each of the scheduled post-baseline treatment phase visits.

IPSS (also called IPSS total score) is the sum of the seven questions. IPSS summaries and analyses will be in terms of the total (score); exceptions will be noted such as for supporting summaries of individual questions. For calculation of the IPSS total, missing individual responses will be imputed when at least four of the seven questions are answered (nonmissing). For the imputation, the average of the nonmissing responses will be calculated and rounded to the nearest integer. This average will be imputed for the original missing response(s). If at least 20% of the subjects have at least one imputed IPSS then the statistical analyses will be repeated based on non-imputed scores.

The efficacy analyses will be based on the Intent-to-Treat (ITT) population. [Table 3](#) provides an overview of the planned IPSS summaries and primary efficacy analyses. A list of planned data displays is in [Appendix 15](#): List of Data Displays.

Table 3 Overview of Planned Primary Efficacy Analyses

Endpoint	Absolute			Change from Baseline			% Change from Baseline		
	L	F	T	L	F	T	L	F	T
IPSS (International Prostate Symptom Score) Change from Baseline									
Primary Analysis (Month 24 Visit)	Y ^[1]			Y	Y ^[1]	Y	Y ^[2]		
Supporting and Sensitivity Analyses of Primary Endpoint									
Mixed-Model Repeated-Measures (MMRM) Analysis (At Visit)						Y			
IPSS Change from Baseline by Subgroup ^[3]						Y			
Individual IPSS Questions	Y ^[1]		Y			Y			
IPSS Percentage Change from Baseline							Y ^[1]		Y
IPSS Non-imputed Score Analysis ^[4]			Y		Y	Y			
IPSS Per-Protocol Population Analysis ^[5]			Y		Y	Y			

NOTES :

- T = Table, F = Figure, L = Listing, Y = Yes display generated. All outputs are based on ITT population except [4].
- Tables and figures have separate outputs for LOCF and At Visit, except for baseline summaries.
- 1. Individual questions 1 – 7 responses, total score, total score change from baseline, and percentage change from baseline are combined in a single listing and presented for every visit.

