8.1.4. Maximum Urine Flow (Qmax)

Qmax and associated total voided volume are measured at screening (Visit 1a with possible repeat at Visit 1b), baseline, and at each Month 6, Month 12, Month 18, and Month 24 (or end of treatment) visits. Qmax change from baseline is a secondary efficacy endpoint. Qmax measurements with voided volumes <125 ml will not be included in the analysis.

[Table 4](#) provides an overview of the planned Qmax summaries and analyses. A list of planned data displays is in [Appendix 15](#): List of Data Displays. Baseline, change from baseline, and percentage change from baseline are defined in [Appendix 6](#). Last observation carried forward (LOCF) and At Visit approaches are defined in [Appendix 7](#). Summaries and analyses will be in terms of the ITT population; LOCF approach will be considered primary. Qmax summary statistics will be presented for each scheduled visit; change from baseline and percentage change from baseline will be presented for each scheduled post-baseline visit.

Change from baseline Qmax at each scheduled post-baseline assessment will be compared in terms of combination treatment versus tamsulosin treatment using t-tests from a general linear model (GLM) with effects for treatment, cluster, and baseline Qmax. Two-sided tests at 0.05 level of significance will be conducted.

The adjusted mean estimates (mean and standard error), the adjusted mean difference, and the 95% confidence interval in terms of the adjusted mean difference will be presented. The adjusted mean difference will be in terms of combination treatment minus tamsulosin treatment. The model results will be presented on same tabular summary as the arithmetic mean, standard deviation, median, minimum and maximum. The results will be presented by treatment for each scheduled post-baseline assessment.

Qmax adjusted mean change from baseline will be plotted by treatment for each post-baseline scheduled visit in terms of each LOCF and At Visit approach.

Qmax improvement is also assessed using categorical changes. Improvement is a post-baseline Qmax which is higher than the baseline Qmax. Worsening is a post-baseline Qmax which is lower than the baseline Qmax. The number and percentage of subjects with Qmax percentage change from baseline categories of 1) improvement, 2) no change, and 3) worsening will be summarized by treatment group using both the LOCF and At Visit approaches at each scheduled post-baseline assessment.

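### The BII imputation rule ignores unequal item ranges and can give a total of 15 or more on a scale that the SAP ends at 13

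*SAP*

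**What the plan says.** Section 8.3.1 describes the instrument in two sentences: "The BPH Impact Index (BII) consists of four questions", and "The BII total score is the sum of the four questions; the total score range is 0 to 13". It does not give the range of each question.

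The same section allows a total to be calculated once two of the four questions are answered, so up to two may be filled in. For those, "the average of the nonmissing responses will be calculated and rounded to the nearest integer", and the one rounded value is placed in each missing item. No cap at the item's maximum is mentioned, and no rescaling. Appendix 7 (Section 11.7.3) only points back to this text.

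A repeat on non-imputed scores is conditional: "If at least 20% of the subjects have at least one imputed BII". BII change from baseline is listed as a secondary health outcome in Section 2.2. It is tested in a general linear model with baseline BII as a covariate, and Appendix 7 makes LOCF the primary approach.

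**The concern.** Filling a gap with the mean of the other answers presumes that all items run over the same scale. The SAP states such a common scale for IPSS (each item 0 to 5, Section 7.1.1) and for PAS SFI (each item 0 to 4, Section 8.3.3). For BII its own figures rule this out, because 13 is not divisible by 4. A raw mean can then exceed what a narrow item allows, and it can fall short of what the widest item would carry.

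An out-of-range or compressed total at baseline enters every change score for that man, and the covariate as well. At a last visit before withdrawal it is carried forward to Month 24. The rule is the same in both arms and nothing in the SAP suggests that it favours one. What is at stake is the validity of individual scores on a tested secondary endpoint, not a directional bias in the treatment comparison.

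**Working it through.** **Inputs (Section 8.3.1).** Four items; total 0 to 13; at least two answered; imputed value = rounded raw mean of the answered items, used in each gap.

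**Assumptions.** Items are whole numbers starting at 0. Where a specific split is needed, the item maxima are taken as 3, 3, 3 and 4, the most even split of 13.

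**1. The stated range on a complete form.** 3 + 3 + 3 + 4 = 13, so the SAP's maximum holds when nothing is missing.

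**2. Two items missing.** One narrow item and the wide item are answered at their maxima, 3 and 4. Mean = 7 / 2 = 3.5, rounded to 4. Total = 3 + 4 + 4 + 4 = 15. Both missing items have a maximum of 3 and both receive a 4. Rounding halves up and rounding halves to even both turn 3.5 into 4. Only a rule that rounds halves down would keep this case at 13, and the SAP states no tie rule.

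**3. Any split.** Let S be the sum of the two largest item maxima. The other two maxima add up to 13 − S, which cannot exceed S, so S ≥ 6.5 and therefore S ≥ 7. With those two items answered at maximum and the others missing, the total is S + 2 × round(S / 2) ≥ 7 + 2 × 4 = 15. Enumeration of all 18 splits of 13 into four positive whole-number maxima gives highest totals from 15 (only for 3/3/3/4) to 23. The overflow does not depend on the assumed split; the exact figure of 15 does.

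**4. One item missing (3/3/3/4).**
- Narrow item missing, the rest at maximum: mean = 10 / 3 = 3.33, rounded to 3; total 13. No overflow.
- Wide item missing, the three narrow items at maximum: mean = 3; total 3 + 3 + 3 + 3 = 12. Proportional scoring gives 13 × 9 / 9 = 13.

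**5. How many patterns exceed 13 (3/3/3/4).** Two answered: 3 × 16 + 3 × 20 = 108 patterns. Three answered: 64 + 3 × 80 = 304. Together 412. Only 3 exceed 13: the wide item and one of the three narrow items, both at maximum, with the other two missing. This counts patterns and is not a probability.

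**6. Distance from proportional scoring (3/3/3/4, halves rounded up).** It runs from −1.1 to +2.0 points. The low end is the three narrow items summing to 7: 7 + 2 = 9 against 13 × 7 / 9 = 10.1. The high end is step 2: 15 against 13 × 7 / 7 = 13.

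**7. Which part of the rule causes it.** Dropping only the rounding in step 2 gives 3 + 4 + 3.5 + 3.5 = 14, still above 13. The unequal ranges have to be handled; the rounding only adds to the excess.

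**The case against.** The best defence is that this hardly ever matters. Under 3/3/3/4, exceeding 13 needs exactly two missing items and maximum answers on the other two. The planned displays would also expose it: Table 4.1 summarises BII imputations, minimum and maximum are tabulated, and item and total scores are listed. This stands as a limit on importance. It does not remove the defect, since a display reveals an impossible score without correcting it.

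A reader might infer three stronger points, which the SAP does not support.

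- *That the same rule damages IPSS, the primary score.* With three of seven items imputed, rounding can move the total by up to 3 × 0.5 = 1.5 points against 7 × the mean of the answered items; for example, an answered sum of 10 gives 19 instead of 17.5. But the unrounded figure is an alternative convention, not a true score. IPSS items share the range 0 to 5, so a rounded mean is always a valid answer and the total cannot exceed 35. Nor is there a general upward drift. With answered sums weighted equally and halves rounded up, the average shift is +0.36 with three items missing, 0 with two and +0.08 with one. With halves rounded to even it is −0.07 with three missing.
- *That PAS SFI has the same fault.* Its items are all 0 to 4, its total cannot exceed 12, and rounding moves it by at most 0.5.
- *That the 20% condition for the non-imputed repeat will normally not be met.* The SAP gives no rate of missing items. The condition counts subjects with any imputed score, not forms. With ten administrations (screening, baseline and eight visits), and assuming independent forms, about 2.2% of forms imputed would reach it: 1 − 0.978^10 = 0.20. What does hold is that, if the condition is not met, an out-of-range total stays in the analysis uncorrected.

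**Conclusion.** The point holds for BII. Section 8.3.1 states a range that its own imputation rule can break: 15 if the item maxima are 3/3/3/4, and at least 15 under any whole-number split, given either of the two tie rules in step 2. Under 3/3/3/4 it also scores a man 12 instead of 13 when the widest item is missing and the other three are at maximum. These are worst cases for single forms. The number affected is probably small, but that is a judgement, because the SAP gives no item-missingness figure. No effect on the treatment difference has been shown. This is a minor scoring defect in a tested secondary endpoint, worth correcting because correction is cheap. It is not grounds for changing how IPSS or PAS SFI is scored.

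**What to change.** Amend Section 8.3.1 for BII only. State the maximum of each of the four items, then use one of the following:

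- **Preferred:** with at least two items answered, BII total = 13 × (sum of answered items / sum of the maxima of those items). This keeps every total within 0 to 13 and removes the under-scoring when the widest item is missing.
- **Minimum:** keep the rounded mean but cap each imputed value at that item's maximum. In step 2 this gives 3 + 4 + 3 + 3 = 13. It does not repair the score of 12 when the widest item is missing.

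The cost is a line of SAP text, the item maxima, and a small change to the derivation code. Proportional scoring makes BII totals on imputed forms non-integer; Section 8.3.1 plans no BII point categories that this would disturb.

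The unrounded approach should not be extended to IPSS. Section 8.1.2 and Table 4 use improvement levels of at least 1 to at least 5 points plus no change and worsening, so an improvement of 0.5 points would fit none of them. The 20% condition can stay as it is.

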8.3.2. BPH-Related Health Status

BPH-Related Health Status (BHS) is collected as Question 8 the IPSS questionnaire and ranges from 0 to 6. The IPSS questionnaire is administered, and thus BHS is collected, at screening, baseline and at each of the scheduled post-baseline treatment phase visits.

Total BHS, change from baseline BHS, and percentage change from baseline BHS will be summarized by treatment group using both the LOCF and At Visit approaches at each scheduled post-baseline assessment. Change from baseline BHS at each scheduled post-baseline assessment will be compared in terms of combination treatment versus tamsulosin treatment using t-tests from a general linear model (GLM) with effects for treatment, cluster, and baseline BHS. Two-sided tests at 0.05 level of significance will be conducted.

The adjusted mean estimates (mean and standard error), the adjusted mean difference, and the 95% confidence interval in terms of the adjusted mean difference will be presented. The adjusted mean difference will be in terms of combination treatment minus tamsulosin treatment. The model results will be presented on same tabular summary as the arithmetic mean, standard deviation, median, minimum and maximum. The results will be presented by treatment for each scheduled post-baseline assessment.

BHS adjusted mean change from baseline will be plotted by treatment for each post-baseline scheduled visit in terms of each LOCF and At Visit approach.

A listing of BHS data will be presented.

As a supportive analysis, BHS will be analyzed using a mixed-model repeated-measures (MMRM) analysis in a manner similar to that described for primary efficacy in [Appendix 13](#).

8.3.3. Problem Assessment Scale of the Sexual Function Inventory (PAS SFI)

The Problem Assessment Scale of the Sexual Function Inventory (PAS SFI) consists of three questions each with a range of 0 (Big Problem) to 4 (No Problem). It is administered at screening, baseline and at each Month 12 and Month 24 (or end of treatment) visits. The total PAS SFI is the sum of the three questions; the total score range is 0 to 12. PAS SFI summaries and analyses will be in terms of the total (score); exceptions will be noted such as for supporting summaries of individual questions.

For a given subject and visit, calculation of the PAS SFI total will not be performed or imputed if two or all three individual responses are missing. For a given subject and visit, a single missing individual response will be imputed when two of the three questions are answered (nonmissing). For the imputation, the average of the nonmissing responses will be calculated and rounded to the nearest integer. This average will be imputed for the original missing response. If at least 20% of the subjects have at least one imputed PAS SFI then the statistical analyses will be repeated based on non-imputed scores.

Total PAS SFI and change from baseline PAS SFI will be summarized by treatment group using both the LOCF and At Visit approaches at each scheduled post-baseline assessment. Change from baseline PAS SFI at each scheduled post-baseline assessment will be compared in terms of combination treatment versus tamsulosin treatment using t-tests from a general linear model (GLM) with effects for treatment, cluster, and baseline PAS SFI. Two-sided tests at 0.05 level of significance will be conducted.

The adjusted mean estimates (mean and standard error), the adjusted mean difference, and the 95% confidence interval in terms of the adjusted mean difference will be presented. The adjusted mean difference will be in terms of combination treatment minus tamsulosin treatment. The model results will be presented on same tabular summary as the arithmetic mean, standard deviation, median, minimum and maximum. The results will be presented by treatment for each scheduled post-baseline assessment.

Each of the three PAS SFI individual question responses will be summarized at Baseline, Month 12, and Month 24 by treatment group. Month 12 and Month 24 changes from baseline will be summarized by treatment group for each of the three questions. The summaries will be based on the ITT population and presented using both LOCF and At Visit approaches. No statistical testing will be performed.

A listing of PAS SFI data will be presented.

9. COUNTRY-SPECIFIC SUMMARIES AND ANALYSES

Four countries randomized subjects into this trial and include: China, Japan, Korea, and Taiwan. It is anticipated that each of these countries will conduct a regulatory submission using planned summaries and analyses of this ARI114265 study. For primary regulatory filings, summaries and analyses will be in terms of the Intent-to-Treat population which is based on pooled country data. These regulatory filings may also require complete or various sub-levels of data summaries and analyses for (their) specific country.

Each country's regulatory requirements will be fully defined at a time approaching the regulatory filing which will be after RAP finalization. Therefore, to address the *potential* requirements for complete country-specific summaries and analyses, all planned tables and figures, including planned statistical analyses, will be repeated for each of the four countries. Cluster (defined earlier in RAP as equal to country) will be excluded from the model-based within-country analysis. Exceptions will include planned by-country tabular summaries and listings. There will be no across-country multiplicity adjustments. The within-country statistical analyses will be underpowered because of their smaller sample sizes.

The summaries and analyses for each of the four countries will be provided by Clinical Statistics and Programming as part of a secondary (country-based) statistical analysis complete (SAC) package. Then, considering country regulatory filing plans and requirements, GSK regulatory staff of the individual countries will indicate to medical writing staff the summaries, analyses, and formats to be used in final reporting. Non-reporting of some or all country-based summaries and analyses by the individual countries will not result in a RAP revision.

It is anticipated that analysis and reporting of each country will add up to 2 weeks to the initial (Intent-to-Treat Population) SAC. Therefore, the "Country-specific SAC" will be "Primary SAC" plus 8 weeks. The country analysis may be ordered so that the country with earliest regulatory requirements will undergo first analysis and reporting. Changes to the anticipated '8 weeks' as well as action definition of country reporting order will not result in a RAP revision.

11.1. Appendix 1: Exclusions from the Per-Protocol Population

In accordance with SOP-130050 and the ARI114265 PDMP, deviations which require exclusion from the Per-Protocol population must be identified, when possible, in advance of treatment unblinding. The deviation review and programming processes, as well as spreadsheet and database capabilities, require that deviation identification must be made from two sources:

1. Study Team Assessment of deviations tracked on study team's protocol deviations spreadsheet and then indicated as 'Exclude from Per-Protocol'
- and
2. Programmatic Assessment which outputs deviations through Statistics & Programming electronic SAS code execution.

The below table lists the 19 deviations which would exclude a subject from the Per-Protocol population along with identification methods. It is expected that a final analysis dataset will be generated with the two sources pooled. Details on the pooled dataset programming and any adjudication process required to reconcile the two sources will be defined in advance of database freeze through a RAP amendment or a high level note to Study File. If there is inconsistency between the two sources, it is anticipated that the programmatic determination will be considered definitive; this will be outlined through a RAP amendment or a high level note to Study File.

Number	Per-Protocol Deviation	Study Team Assessment	Programmatic Assessment [eCRF Code Note a]
01	Missed placebo run-in phase	Any evidence which implies or documents that subject missed the placebo run-in phase.	1) Placebo run-in treatment start and stop dates are missing or 2) Placebo run-in tablets consumed = zero [A5]
02	Incorrect study drug (wrong treatment) consumed	Any evidence which confirms that the incorrect container contains other-than-scheduled study treatment.	Treatment consumed (from incorrect dispensed container) unequal to treatment planned in randomization schedule. Note: this can only be determined after study unblinding. [A5]
03	Randomized but did not consume double-blind study drug	Any evidence which confirms that the zero tablets were consumed in double-blind phase	Final nonmissing cumulative study drug compliance = zero [A5]
04	Cumulative study drug compliance <75%	Study team is unable to calculate RAP-defined study drug compliance. Therefore, deviation will be determined based on programmatic	Final nonmissing cumulative study drug compliance < 75% [A5]

Number	Per-Protocol Deviation	Study Team Assessment	Programmatic Assessment [eCRF Code Note a]
		assessment.	
05	Cumulative study drug compliance >125%	Study team is unable to calculate RAP-defined study drug compliance. Therefore, deviation will be determined based on programmatic assessment.	Final nonmissing cumulative study drug compliance > 125% [A5]
	Violation of Inclusion Criteria (protocol #)		
06	Confirmed BPH clinical diagnosis (Inclusion 2)	Any evidence which confirms inclusion criterion 2 deviation.	Eligibility database indicates violation of inclusion criterion 2 [A1]
07	IPSS \geq 12 at Screening (Inclusion 3)	Any evidence which confirms inclusion criterion 3 deviation.	Eligibility database indicates violation of inclusion criterion 3 [A1]
08	Prostate volume \geq 30cc by TRUS at Screening (Inclusion 4)	Any evidence which confirms inclusion criterion 4 deviation.	Eligibility database indicates violation of inclusion criterion 4 [A1]
09	PSA \geq 1.5ng/ml and \leq 10ng/mL at Screening (Inclusion 5)	Any evidence which confirms inclusion criterion 5 deviation.	Eligibility database indicates violation of inclusion criterion 5 [A1]
10	Qmax $>$ 5 mL/sec and \leq 15mL/sec with Voided Volume \geq 125mL/sec at Screening (Inclusion 6)	Any evidence which confirms inclusion criterion 6 deviation.	Eligibility database indicates violation of inclusion criterion 6 [A1]
	Violation of Exclusion Criteria (protocol #)		
11	Any conditions other than BPH, which may in the judgement of the investigator, result in urinary symptoms or changes in flow rate (Exclusion 6)	Any evidence which confirms exclusion criterion 6 deviation.	Eligibility database indicates violation of exclusion criterion 6 [A1]
12	Use of 5ARI within 6 months of Screening or historical TRUS and throughout the study (Exclusion 10a)	Any evidence which confirms exclusion criterion 10a deviation.	Reference Note b. [A1]
13	Use of anabolic steroids within 6 months of Screening and throughout the study (Exclusion 10b)	Any evidence which confirms exclusion criterion 10b deviation.	Reference Note b. [A1]
14	Use of phytotherapy for BPH within 2 weeks of Screening and throughout the study (Exclusion 10c)	Any evidence which confirms exclusion criterion 10c deviation.	Reference Note b. [A1]

Number	Per-Protocol Deviation	Study Team Assessment	Programmatic Assessment [eCRF Code Note a]
15	Use of alpha-adrenoreceptor blockers within 2 weeks of Screening and throughout the study, except study meds (Exclusion 10d)	Any evidence which confirms exclusion criterion 10d deviation.	Reference Note b. [A1]
16	Use of alpha-adrenoreceptor agonists or anticholinergics or cholinergics within 48 hours prior to all uroflowmetry and IPSS assessments (Exclusion 10e)	Any evidence which confirms exclusion criterion 10e deviation.	Reference Note b. [A1]
17	Use of selective beta 3-adrenoreceptor agonist (mirabegron) within 2 weeks prior to all uroflowmetry and IPSS assessments (Exclusion 10f)	Any evidence which confirms exclusion criterion 10f deviation.	Reference Note b. [A1]
18	Prohibited medications and non-drug therapies of Protocol Section 6.2 and not otherwise classified above.	Study team identification of prohibited medication or non-drug therapy which should require exclusion from per-protocol population and not otherwise classified above.	[A3]
	Other		
19	Any condition which should exclude a subject from the Per-Protocol population and is not include above.	Study team identification through review of multiple sources such as protocol deviation log text, study drug compliance outliers, concomitant medication logs, or site/monitor communications.	NA

Notes:

- Reflects eCRF corresponding code to be applied programmatically; definitions in below table.
- Exclusion 10 subsets (a – f) are not individually identified in the INFORM and Analysis & Reporting datasets. Therefore, deviation will be determined based on study team assessment.

Important Deviations Categories, Subcategories, and eCRF Codes (eCRF Codes define above indicated programmatic assignment)	
Category / Subcategory	eCRF Codes
Assessments and/or procedures	
Biological specimen sample procedures	6E
Equipment procedures	6G
Failure to comply with dosing procedure	6L
Failure to report SAE, pregnancy, or liver function abnormalities per-protocol	6B
Informed consent process	6A
Missed assessment or procedure	6I
Randomization procedures	6H
Study blind / unblind procedures	6C
Study treatment supply procedures	6D
Other	6OT
Eligibility criteria not met	A1
Prohibited medication or device	A3
Received wrong treatment or incorrect dose	A5
Visit, assessment or timepoint window	
Window for dose administration	4C
Window for efficacy assessments	4A
Window for safety assessments	4B
Other	4OT

